10.4.2 Analysis of the Primary Efficacy Endpoint(s)

We will use a repeated measures mixed effects model for analysis of the primary outcome measure (change in interpalpebral fissure during opening and spontaneous blinking). The model will include a random subject-level intercept and a fixed treatment effect (MLP or KTFS). A repeated measures model will be used with primary timepoint for analysis being after 1 week of use. . The model will also include fixed effects of treatment order (i.e., MLP: KTFS vs KTFS:MLP), and crossover period (period 1 or 2), and will control for age and sham opening interpalpebral fissure.

10.4.3 Analysis of the Secondary Endpoint(s)

The change in interpalpebral fissure during volitional blinking will be analyzed using the same approach as for the primary outcome measure. Questionnaire responses will be summarized using descriptive statistics and analyzed using non-parametric tests.

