Outcome measures Primary outcome: Difference between MLP and KTFS in the change in interpalpebral fissure during and spontaneous blinking

Secondary outcome: Difference between MLP and KTFS in the changes in interpalpebral fissure during opening and volitional blinking

Secondary outcome: Proportion of subjects selecting each device at the end of the crossover

Population: Individuals with severe unilateral or bilateral ptosis defined as occlusion of the visual axis by the lid in the resting state

[figure not shown]
Phase: N/A

Clinical Trial to improve the magnetic levator prosthesis (MLP) including the development and testing of a novel adjustable force system and comparison to the Kinesio Tape frontalis sling (KTFS) Version 1

Number of Sites enrolling participants:	1
Description of Study Agent :	Magnetic levator prosthesis (MLP) with compatible spectacle frames
Study Duration:	Kinesio Tape frontalis sling (KTFS)
Participant Duration:	2 to 3 years
	8 or 9 weeks from enrollment to the end of the crossover period of the clinical trial, with an additional 8 weeks after the end of the crossover for subjects who have a clinical decision to participate in the extended wear part of the clinical trial

SCHEMATIC OF STUDY DESIGN

Also, please refer to the study schema:

FU: Follow up

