10.2 Statistical Hypotheses

Primary outcome measure:

Statistics for the participant characteristics will be presented in terms of mean \pm standard deviation or median \pm interquartile range (25th to 75th). Within subjects repeated measurements, linear mixed effects regression will be used to determine the effect of treatment condition on the IPF values (spontaneous and resting state open), with a random intercept for the subject factor. Subject age, gender, blink sequence (the order of the blink recorded in the video), and the order of interventions (whether evaluated in the first or the second arm of the crossover) will be covariates of interest. Effect of each covariate will be investigated alone, and only statistically significant ($P < .05$) covariates will be included in the final regression model, from which, the estimated marginal means and their 95% confidence interval (CIs) will be reported for each of the outcomes. Missing values at the T2 time point will be imputed from another time point within the same subject (T1 by default or T0 if both T1 and T2 were not available). For volitional blinks, a test of proportionality will be performed to determine the effect of the 3 treatments on the probability of eye not fully closing.

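### Section 10.2 gives volitional blinks a three-treatment test of incomplete closure, which does not match the MLP-KTFS change in interpalpebral fissure named as the secondary outcome in the Protocol Summary and 10.4.3

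*Combined protocol and SAP*

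**What the plan says.** The outcome measures in the Protocol Summary include "Secondary outcome: Difference between MLP and KTFS in the changes in interpalpebral fissure during opening and volitional blinking". Section 10.4.3, which covers the secondary endpoints, states: "The change in interpalpebral fissure during volitional blinking will be analyzed using the same approach as for the primary outcome measure".

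The primary approach is in 10.4.2: "The model will include a random subject-level intercept and a fixed treatment effect (MLP or KTFS"). The same section fixes the time: "A repeated measures model will be used with primary timepoint for analysis being after 1 week of use".

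Section 10.2 divides the work differently. There, "linear mixed effects regression will be used to determine the effect of treatment condition on the IPF values (spontaneous and resting state open"). Volitional blinks are not in that list. They get a test of proportionality for the "effect of the 3 treatments on the probability of eye not fully closing".

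Section 4.1 describes a comparison of two treatments, and 7.3.2 randomises to two orders of MLP and KTFS. Section 7.3.2 also describes a recording with a sham MLP, as a baseline measure taken during training, and says that no sham KTFS recording is possible.

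**The concern.** The Summary and 10.4.3 give one analysis of volitional blinks and 10.2 gives another. They differ in the variable (a continuous change in IPF, or a yes/no for incomplete closure), in the comparison (two devices, or three unnamed conditions) and in the method (a mixed model, or a test of proportions). Nothing in 10.2 says that its test adds to the 10.4.3 analysis. Because its mixed model omits volitional blinks, 10.2 read alone replaces that analysis.

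At stake is a choice between two differently defined results after the data are seen. Little in the plan closes off that choice: 10.4.7.2 allows periodic preliminary analyses, and 10.4.9 has no plan for multiple comparisons. The outcome matters clinically, since section 2 raises incomplete blinking with the MLP and incomplete eye closure with skin tape.

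**Working it through.** **The texts side by side**

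| | Summary, 10.4.3 and 10.4.2 | 10.2 |
|---|---|---|
| Variable | Change in IPF | Eye not fully closed, yes/no |
| Conditions | MLP, KTFS | Three, not named |
| Method | Mixed model, random subject intercept | Test of proportionality |
| Timepoint | After 1 week of use | Not stated for this test |
| Called a secondary outcome | Yes | No |

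If the third condition is the sham MLP, the only sham data described are the baseline recordings in training. A three-way test at 1 week would then have no sham data described for it. A significant three-way result also would not say whether MLP differs from KTFS. No cut-off is given for full closure, and 10.4.1 allows manual, automated or crowdsourced reading.

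**Can the two analyses favour opposite devices?**

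The plan gives no effect size, standard deviation or power for this outcome, so there is no figure to reproduce. Its sample size of 16 (10.5) is for the primary outcome and is used here only as the number of people. All blink values below are assumptions.

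Let p be the proportion of blinks not fully closed and g the mean gap on those blinks. The mean residual IPF is p × g. If both devices are measured against the same no-device baseline, that baseline cancels, and the MLP-KTFS difference in change equals the difference in residual IPF. A smaller residual gap is taken as better.

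- MLP: 0.60 × 0.5 mm = 0.30 mm.
- KTFS: 0.30 × 2.5 mm = 0.75 mm.

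The mean favours MLP by 0.75 − 0.30 = 0.45 mm. The proportion favours KTFS by 60% − 30% = 30 percentage points. With these frequencies, the directions are opposite only if the gap ratio exceeds 0.60 / 0.30 = 2. Here it is 2.5 / 0.5 = 5.

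Reversal does not depend on which device leaves the small gaps. If device A leaves 20% of blinks open by 4 mm, its mean is 0.80 mm. If device B leaves every blink open by 0.5 mm, its mean is 0.50 mm. The mean favours B and the proportion favours A.

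**How often would both be significant in opposite directions?**

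The simulation used 4,000 trials of 16 people with 10 blinks per device, and a person-level SD of 0.15 in the probability of incomplete closure. Gaps were gamma-distributed. Paired t tests at 0.05 were run on person means and on person proportions. The base case has a person effect shared by both devices, gamma shape 4 and no between-person variation in gap size.

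| Assumptions | Both significant, opposite directions |
|---|---|
| Base case, KTFS gap 2.5 mm (ratio 5) | about 96% |
| Gamma shapes 1 to 25 | about 83% to 98% |
| Person effects independent between devices, shapes 1 to 4 | about 72% to 87% |
| Between-person log-SD of gap size 0.5 | about 74% |
| Between-person log-SD of gap size 0.8 | about 41% |
| KTFS gap 1.5 mm (ratio 3) | about 46% |
| KTFS gap 1.0 mm (ratio 2, mean gaps equal) | about 2% |
| KTFS gap 0.5 mm (equal gap sizes) | 0% |

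Each row changes only the item named. The result depends mainly on the gap ratio, about which the documents say nothing.

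**The case against.** A reader might infer that no volitional-blink secondary endpoint is named, or that the plan has no lead definition. The documents do not support that. The Summary labels the continuous MLP-KTFS outcome as secondary, and 10.4.3 analyses the same variable under the secondary-endpoint heading. Section 10.2 never calls the proportion an outcome or endpoint, and its sentence stands under a primary-outcome label. It may have been meant as an additional analysis of the same blinks. This part of the objection stands. It does not settle the matter, because 10.2 does not say so and its mixed model omits volitional blinks.

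A reader might also infer from the 96% that contradictory results are likely. The table rules that out as a general statement: reversal needs many small gaps on one device and fewer large gaps on the other, and with equal gap sizes it does not occur.

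Nor is this outcome the trial's most direct evidence on corneal exposure. The schedule has slit-lamp examination with NEI grading at Visits 1 to 8, and 8.1 sets corneal-rating cut-offs with independent review. Masking of assessors and analyst (10.6.1) gives some protection against selective reporting, but it is described for the primary outcome.

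Finally, not fully closing can be read plainly as any gap at all. That is workable, but with three permitted reading methods the smallest gap that counts still needs to be fixed.

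**Conclusion.** The point holds as an inconsistency between stated rules. The Summary and 10.4.3 name a continuous MLP-KTFS outcome in the two-level model; 10.2 gives the same blinks a three-treatment test of incomplete closure, with the third treatment unnamed and no sham data described beyond baseline. That test does not address the stated MLP-KTFS question.

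The effect on conclusions cannot be sized from the documents. Under the assumed inputs, opposite significant results run from 0% with equal gap sizes to about 96% in the base case with a fivefold gap ratio. This shows possibility, not likelihood. The outcome is secondary and the correction is cheap, so it should be made before unmasking.

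**What to change.** Amend 10.2 to agree with the Summary and 10.4.3. The volitional-blink secondary endpoint is the MLP-KTFS difference in change in IPF during volitional blinking, at the 1-week timepoint, from the 10.4.2 model, with the direction of benefit stated. Keep the plan's own variable, and leave the opening component of the Summary's secondary outcome as it is.

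Keep the proportion of volitional blinks not fully closing as a labelled supportive outcome for the same contrast and timepoint. Fix the closure cut-off before unmasking, and always report the proportion beside the IPF result. If a third condition is compared, name it and keep that comparison descriptive.

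The cost is a change of wording; the same recordings serve. The downside is that the proportion test becomes supportive.

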10.4.4 Safety Analyses

Clinical study staff will acquire high resolution magnified images of the ocular surface and eyelid skin which will be reviewed by the PI and at least 1 other study team member with clinical training will produce quarterly reports to be reviewed by the independent safety monitor. On-site monitoring of participant safety will be utilized by the PI or other study personnel. This is appropriate since problems can be immediately detected and addressed by research staff experienced in examination of the eye. A monitoring log of expected and unexpected events will be kept. Events will be documented on paper and sent to the PI (if he is not the one examining the participant) who will place a follow-up call to the participant that day and the next day as needed. Paper documentation will be kept in the study binder and then transferred to a worksheet in the study master spreadsheet. Non-compliance with protocol (e.g. failure to use the study checklist or properly document or report in a timely manner adverse events) will be documented. Once identified, minor issues will be addressed by the PI by special meeting or at weekly study meetings. Special meetings will be called depending on the seriousness of the issue. Repeated offenses will result in removal of that study staff from the protocol. Adverse events will be documented and reported to the IRB and NEI per protocol.

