7 STUDY PROCEDURES AND SCHEDULE

7.1 Study Procedures/Evaluations

7.1.1 Study specific procedures

The following procedures will be performed as part of the study (see schedule of events table in section 7.3.7.)

1. Refraction (if needed)
2. Visual acuity
3. Slit lamp examination of external eye, lid and cornea with Nafl & NEI scale
4. Comfort rating
5. Video recording of eye blinks
6. Rating of skin integrity
7. EQ-5D-5L questionnaire
8. GBI questionnaire
9. aQoL questionnaire

Based on experience, we anticipate that the first study visit will typically last about 120 minutes and subsequent visits about 60 minutes.

Some of the visits will be conducted virtually (as detailed in subsequent sections). To facilitate virtual visits, a visual acuity chart will be given to the subject to allow this safety outcome monitoring remotely and other safety outcomes will be conducted during the call (comfort scale, inspection of the external eye and lid skin).

Detailed plan for REDCap text message and email communication:

A short three-question survey will be used to document whether subjects are wearing a device during the periods of home use. Consent to receive a survey link by text message or email will be documented in the consent form along with the preferred contact method (text, email, or both). For subjects that consent to receive the survey links, their preferred phone number and/or email address will be recorded on a sheet separate from the consent form, which will be kept in a locked cabinet in a locked office. As soon as the phone number and/or email address have been input into REDCap, the original will be shredded.

Subjects who consent to receive the survey links will receive a text message or email (based on their communication preference) with a link to a REDCap survey twice daily when using one of the devices at home during the trial week. Please see uploaded document for details of the survey language and questions. Subjects will be able to decline receiving the survey links at any time.

Text message plan: Text messages will be sent to subjects using the Twilio platform. The “Survey as webpage” option will be selected so that subjects can access the REDCap survey URL directly from the text. Subjects’ phone numbers will only be entered if they consented to receiving messages in this way. A sentence in the text message will notify the subject that they can opt out of receiving these texts by replying “Stop”.

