7.3.7 Schedule of Events Table

*Visits 8-10 are in office, approximately every second week. There will be video

		Consent	EQ-5D-5L Questionnaire	aQoL Questionnaire	GBI Questionnaire	Visual Acuity	SlitLamp, skin rating, & NEI grading	Video Recordings & Comfort ratings	Application & Removal training	Debrief and device comparison questionnaire	Clinical decision
Device 1	Visit 1	x	x	x		x	x	x	x		
	Visit 2					x	x	x	x		
		About 1 week wearing at home with video calls for safety monitoring and daily survey about wear time									
	Visit 3		x	x	x	x	x	x			
	Washout (about 2 weeks)										
Device 2	Visit 4		x	x		x	x	x	x		
	Visit 5					x	x	x	x		
		About 1 week wearing at home with video calls for safety monitoring and daily survey about wear time									
	Visit 6		x	x	x	x	x	x			
	End of crossover period										
	Phone call									x	
	Visit 7					x	x	x			x
	Start of extended wear trial (about 6 months)										
Chosen device											
	Visit 8		x	x	x	x	x	x			
	Long term follow up										
	6 month phonecall		x	x	x						
	12 month phonecall		x	x	x						

call follow ups on weeks without an in-office visit

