8 ASSESSMENT OF SAFETY

8.1 Specification of Safety Parameters

The safety of the study devices will be evaluated at every visit following the enrollment visit and will be defined by the incidence of related adverse events. Specifically, we will evaluate:

10. **Systemic safety:** Incidence and severity of systemic adverse events during the study (adverse events spontaneously reported or observed by the Research Assistant).
11. **Ocular safety:** Incidence and severity of ocular adverse events during the study (ophthalmic examination, adverse events spontaneously reported).

SAFETY CUTOFFS: Serious adverse events which would result in study suspension: Should visual acuity decrease more than 2 lines, worsening of corneal rating of more than 1.5 points or other ocular surface ratings more than 2 points, and comfort rating lower than 5/10; study activities will cease for at least 1 week and an adverse event report will be sent to the IRB. Corneal rating changes >1.5 points will be reviewed by the independent safety monitor at the Eye and Ear to determine if criteria for study suspension or dismissal are met, and when it may be possible to continue. Serious adverse events which will result in immediate dismissal from the study (and treatment) include: 1) development of a related corneal ulcer (as judged clinically by the independent safety monitor) with or without infiltrate or 2) broken skin on the eyelid (skin decompensation).

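### Corneal, lid-skin, comfort and acuity grades are scheduled on both devices, but the plan has no analysis of them: safety analysis stops at adverse-event incidence and severity

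*Combined protocol and SAP*

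**What the plan says.** Section 7.1.1 lists among the study procedures "Slit lamp examination of external eye, lid and cornea with Nafl & NEI scale", and separately a comfort rating, a skin rating and visual acuity. The schedule of events (section 7.3.7) marks the columns "SlitLamp, skin rating, & NEI grading" and "Video Recordings & Comfort ratings", together with visual acuity, at Visits 1 to 3 (first device) and Visits 4 to 6 (second device). They are marked again at Visits 7 and 8, after the crossover.

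Section 8.1 says that device safety "will be defined by the incidence of related adverse events". The ocular component is "Incidence and severity of ocular adverse events during the study", with the ophthalmic examination and spontaneous reports as sources. The grades then appear as triggers for an individual participant: an acuity loss of more than 2 lines, and "worsening of corneal rating of more than 1.5 points or other ocular surface ratings more than 2 points, and comfort rating lower than 5/10". Corneal changes beyond 1.5 points go to the independent safety monitor.

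Section 10.4.4, Safety Analyses, covers review of ocular-surface and lid-skin images by staff who "will produce quarterly reports to be reviewed by the independent safety monitor", an event log, and the handling of non-compliance by study staff. It gives no estimate, model, test or interval.

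**The concern.** The harms the protocol expects are matters of degree. The risk section describes ocular surface drying and discomfort from a slow or incomplete blink with the MLP; for the tape it describes drying, discomfort and skin irritation. Section 2.1 complains of how little safety data exist on taping, and section 2.2 gives confirming safety as one reason for the research.

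A crossover suits this question well, because a completer is graded on both devices. If the plan is followed as written, those grades are reduced to adverse events and individual cut-offs. The trial could then end with no planned estimate of which device is harder on the cornea or lid skin, although the data to make one had been collected. An estimate chosen after the results are known would carry less weight.

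**Working it through.** **1. Does any section analyse the grades?**

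| Section | What it covers | Device comparison of grades? |
|---|---|---|
| 8.1 | Adverse-event incidence and severity; individual cut-offs | No |
| 10.4.1 | Descriptive statistics for primary and secondary endpoints; the grades are neither | No |
| 10.4.3 | Volitional blinking and questionnaires; section 7.1.1 lists comfort and skin ratings apart from the questionnaires | No |
| 10.4.4 | Image review, quarterly reports, event log | No |
| 10.4.5 | Periodic summaries, including safety issues | No |
| 10.4.6 | Baseline descriptives, so at most the starting grades | No |
| 10.4.11 | States that there are no exploratory analyses | No |

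**2. What a cut-off can miss.** Suppose every participant's corneal grade worsened by 1 point on one device and 0 on the other. The devices would differ consistently, yet nobody would pass the 1.5-point trigger. Some of these changes might be logged as adverse events, since section 8.1.1 includes abnormal signs, but section 8.2 leaves that to case-by-case judgement.

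**3. The plan's own sample size.** Section 10.5 gives 16 as the number required for the primary outcome at power 0.80 and 0.05. It states no SD or interim effect, so the 16 cannot be reproduced. Solving backwards with a two-sided paired t-test at n = 16 gives a standardised difference of 0.749; the normal approximation gives (1.960 + 0.842)/√16 = 0.700. The earlier plan of 40 completers plus 10 for attrition gives the stated 50. None of these figures was set for safety.

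**4. Precision of event counts, with 16 as an illustrative denominator.** Upper 95% limit after 0 events in n = 16:
- Exact, two-sided: 1 − 0.025^(1/16) = 20.6%
- Wilson, two-sided, with z² = 3.84: 3.84/(16 + 3.84) = 19.4%
- Rule of three: 3/16 = 18.75%
- Exact, one-sided: 1 − 0.05^(1/16) = 17.1%

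With 1 event in 16, the exact limits rise to 30.2% (two-sided) and 26.4% (one-sided). The chance of seeing no event at all is 0.95^16 = 44% if the true risk is 5%, and 0.90^16 = 19% if it is 10%; both risks are assumed.

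The number exposed to each device is not stated. If it were 20, the exact two-sided limit for no events would be 1 − 0.025^(1/20) = 16.8%. At 50, the original enrolment target, it would be 7.1%.

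**5. Precision of a paired comparison of grades.** With 16 complete pairs and period adjustment (14 degrees of freedom), the 95% half-width for a mean difference is t(0.975, 14)/√16 = 2.145/4 = 0.54 SD of the within-person difference. Power of 80% is reached at about 0.75 SD (the t-test result in step 3). The documents give no SD for any grade, so neither figure converts to grade points. Both treat the grade as continuous and only approximate what an ordinal method would give.

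**The case against.** The strongest reply is that the grades are used. They trigger a pause and a report to the IRB, large corneal changes go to the independent safety monitor, images are reviewed by the PI and at least one other clinically trained team member, and severity is reported as well as incidence. All of this stands. A reader might infer that safety is judged on counts alone, or that the grades are wasted; section 8.1 contradicts both. What remains is narrower: these are monitoring uses, one participant at a time, and none yields a device comparison.

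Four further inferences are tempting and not supported:
- **That the trial cannot exclude a harm affecting one person in five.** With no events in 16, only the two-sided exact limit passes 20%; the other three conventions in step 4 fall below it. Sixteen is also not the number exposed. Section 10.5 originally planned to enrol 50, and section 10.6.1 reports more subjects than anticipated.
- **That counts would almost always show no difference.** The documents give no event risks and plan no test of counts. Adverse events include any abnormal sign (8.1.1) and mild lid discomfort is recorded (10.4.7.1), so counts need not be near zero.
- **That a paired interval is narrow enough to judge against the 1.5-point trigger.** The interval describes a mean difference; the trigger describes one participant's worsening. A small mean difference can coexist with individuals beyond the trigger.
- **That every participant will have clean start and end grades on both devices.** Dismissal for a related corneal ulcer or broken lid skin (8.1) can remove the worst outcomes. Those who do not pass application training take no device home (7.3.2). Up to 10 participants may be examined remotely with a Burton lamp (7.10). The schedule does not say whether the Visit 1 and Visit 4 grades precede device placement.

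The last point does not remove the gap, but it rules out a simple complete-pairs comparison of Visit 1 to 3 with Visit 4 to 6, which could favour the more harmful device.

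**Conclusion.** The concern holds in this form: four graded safety measures are scheduled in both device periods, the planned safety analysis is adverse-event incidence and severity, and no section plans an MLP-KTFS comparison of the grades or any summary beyond baseline. The finding rests on the text and does not depend on the sample size; a larger denominator would tighten the event counts and still leave the grades unanalysed.

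The size of the loss can only be illustrated. Event counts with no events in 16 leave an upper limit of about 17% to 21%, less if more people were exposed. A paired comparison would itself be modest, with 80% power only for differences of about 0.75 SD, so it should be read as estimation. The efficacy conclusion is not affected. The change is still worth making, because relative safety is part of the trial's stated rationale and the data are already scheduled.

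**What to change.** Add to section 10.4.4:

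1. **Outcome.** For each device, change in NEI corneal grade, skin rating, comfort and visual acuity, from the period-start grade taken before device placement (Visits 1 and 4) to the last or worst grade on that device. Choose last or worst in advance. The end point is Visit 3 or 6, or the last assessment before early removal or dismissal.
2. **Comparison.** Within subject, adjusted for period, using a rank-based or other method suited to ordinal grades. Report the MLP-KTFS difference with a 95% interval, labelled as estimation only.
3. **Counts.** Adverse events per device with exact intervals, using the number exposed to that device as the denominator and naming the convention (one- or two-sided).
4. **Dismissals.** Count participants dismissed for corneal ulcer or broken skin as worst outcomes on the device concerned. Someone dismissed in the first period has no value on the second device, so state in advance how that person enters the paired comparison, and show the number.
5. **No home use.** Report, by device, those who never reached home use.
6. **Remote grades.** Show Burton-lamp grades separately or in a sensitivity analysis.

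The cost is SAP wording and analysis time. No new assessment is needed if the Visit 1 and 4 grades are already taken before placement; if they are not, the order within those visits needs to be specified. The downside is a few more descriptive intervals of limited precision, which readers must not take as evidence that the devices are equally safe.
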